## 4.9 Analysis Plan

### 4.9.1 Aim 1 Analytic Approach

Hypotheses 1 & 2 in Aim 1 posit that patients seen at clinics with the SDMT-focused or PCP-focused cancer screening CDS will be more likely than patients seen at UC clinics without the CDS to have appropriate screening for breast, cervical, and colon cancer (H1), and a full course of three HPV vaccinations (H2) within 12 months of an index visit. Because clinics are the unit of randomization and the outcome varies at the level of the patient, generalized linear mixed-model regression with a logit link and binomial error distribution will be used to test the effect of the interventions. The general form of the analytic model for H1 & H2 is:

$$\text{Dependent Variable}_{kji} = \gamma_{00} + \gamma_{100}\text{SDMT\_CDS}_k + \gamma_{200}\text{PCP\_CDS}_k + \gamma_{001}\text{SEX}_i + [\nu_{k00} + u_{kji} + e_{kji}]$$

The dependent variable in each model is a binary indicator of appropriate screening (H1) or complete course of HPV vaccination (H2). The dependent variable is predicted by the two fixed-effect terms representing the study arm contrast (SDMT\_CDS and PCP\_CDS). Patient sex is included as a fixed effect because screening rates for H1 and vaccination rates for H2 are likely to be different. We will screen patient characteristics to determine

whether they differ across study arm and include patient covariates in the model when they are unbalanced by treatment arm. Random terms are included for clinic ( $v_{k00}$ ), provider ( $u_{kj0}$ ), and patient ( $e_{kii}$ ). The provider random term will be removed if the provider intra-cluster correlation (ICC) is less than 0.005. A significant treatment group effect ( $P<0.025$ ) and positive and significant parameters for the treatment group terms  $\gamma_{100}$  and  $\gamma_{200}$  for each hypothesis will support the H1 & H2 predictions that clinics with CDS interventions are more effective than clinics without them for increasing cancer screening and HPV vaccination rates. This model will include patient sex and patient variables unbalanced by study arm as well as the indicated random effects. Treatment group heterogeneity by sex will be assessed by including interaction terms between patient sex and the two study arm indicators.

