**Specific Aim 1.** Conduct a cluster-randomized trial that includes 36 primary care clinics (34 randomized clinic units, with 3 clinics randomized together due to shared providers) with approximately 300 PCPs and more than 153,000 patients to one of three study arms: (a) PCP-Focused Group: PCP intervention using an EHR-linked, Web-based CP-CDS system, (b) shared decision-making tools (SDMT) Focused Group: PCP intervention using an EHR-linked, Web-based CP-CDS system including additional, or (c) usual care (UC) to assess whether this intervention can improve the delivery of evidence-based, personalized primary and secondary cancer preventive care in rural primary care settings. Specifically, the PCP-focused group will receive a point of care CP-CDS tool that is integrated into the EHR. The CP-CDS provides evidenced-based recommendations to the provider and patient related to overdue cancer prevention screening services and eligible for smoking cessation and obesity management referrals. The SDMT-focused group will also receive the CP-CDS. Furthermore, the SDMT-focused arm provides SDMT to the patient and provider at the time of the visit. The UC arm will not receive the CP-CDS or SDMT but will receive usual best practice advisory suggestions for cancer prevention screening and other usual care.

**Hypothesis 1 (H1).** Eligible study subjects will have significantly different rates of appropriate screening tests for breast, colorectal, and cervical cancer as defined by the U.S. Preventive Services Task Force (USPSTF) during the 12 months after the index visit by study arm, with PCP-focused group higher than UC and SDMT-focused group higher than UC.

**Hypothesis 2 (H2).** Eligible study subjects will have significantly different rates of human papilloma virus (HPV) vaccination in appropriate cases, as defined by the Advisory Committee on Immunization Practices/Centers for Disease Control and Prevention during the 12 months after the index visit by study arm, with PCP-focused group higher than UC and SDMT-focused group higher than UC.

**Specific Aim 2.** Assess the cost of the CP-CDS intervention from the health system perspective through measurement of healthcare utilization and use of diagnostic codes and billing levels related to cancer prevention services.

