Several recent developments make EHR-linked Web-based point-of-care CDS for cancer preventive services feasible on a large scale for the first time: (a) over 80% of PCPs now use EHR systems, (b) we have shown in a randomized controlled trial that our EHR-linked, Web-based approach to CDS significantly improves chronic disease care in high-risk adults, (c) this CDS system requires only minor adjustments in clinic workflow and does not slow PCPs down, (d) Web-based algorithms can be easily updated and are highly scalable to both large and small healthcare delivery systems, and (e) previous cost-effectiveness analysis indicates that this approach to CDS is highly cost-effective and may be cost-saving at scale. After adapting previous work to the needs of our new clinical target, we will randomly assign 36 primary care clinics (34 clinic randomization units) to 3 groups (11 intervention clinic units in the PCP-focused group, 11 intervention clinic units in the SDMT-focused group, and 12 usual care control clinic units) with approximately 300 PCPs and more than 153,000 primary care patients. The number of clinic units to be randomized (34) is smaller than the number of clinics in the study (36) due to three small clinics being grouped together. A particular focus in our project is to compare the impact of a PCP-focused CDS workflow with a SDMT-focused CDS workflow.

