**3.3 Study Design:** Supported by CFIR and RE-AIM frameworks, the implementation process for CP-CDS has four phases: a) initial organizational engagement; b) adopting and piloting the CP-CDS with Essentia Health (EH) PCPs and patients; c) a cluster-randomized controlled trial with 3 arms in 36 EH primary care clinics (34 randomized clinic units), and d) evaluation of the implementation process and outcomes. Because three small clinics were randomized together, there are 34 randomized units in this study. Five randomization schemes were developed using random numbers and 1:1:1 allocation to the three study arms. The randomization scheme selected was pre-determined to be the first of five schemes (blind to clinic allocation) with adequate balance on factors of clinic urbanicity, % of patients who were current smokers, % of patients under 30, total number of patient visits per clinic, % of patients with Medicaid, breast cancer screening rate, geographic region, count of patient with serious mental illness, count of patient with pre-diabetes, colorectal cancer screening rate, access to low-dose lung screening, and participation in a community wellness initiative. Quantification of study arm balance was not based on a priori cut-offs but on subjective assessment of balance by the study team.

The two arms were randomly assigned to either the PCP-focused intervention (CP-CDS) or SDMT-focused intervention (CP-CDS + SDMT). The 12-usual care (UC) clinics for the Cardiovascular Wizard studies will continue as control clinics with the CP-CDS (Figure 1) in a 1:1:1 allocation. Because three small clinics were randomized together, there are 34 randomized units in this study.

[figure not shown]
Eligible patients will be allocated to the study arm assigned to their clinic at their index visit.

**3.4 Study Sites:** This study will be conducted at 36 Essentia Health (EH) primary care clinics in North Dakota, Minnesota, and Wisconsin. Leaders at EH are fully committed to the project, as indicated in letters of support from Drs. [name] and [name]. These 36 clinics have used the EpiCare® EHR since 2004 and have, on average, 12 PCPs and 3,996 eligible patients per clinic (range, 318–11,823). Ten participating EH clinics are classified as rural, 7 as micro, 8 as small towns, and 9 as urban by the RUCA2-UR coding system.

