#### **4.6 Implementation of the Cancer Prevention CDS Intervention**

Throughout the implementation of the CP-CDS, we will conduct key informant and patient interviews, surveys, usability testing, and continuous quantitative and qualitative feedback between researchers and participants to measure the implementation processes and outcomes as recommended by the CFIR and RE-AIM frameworks. **Organizational Engagement:** In Phase 1, we will engage EH clinic leadership and managers, informatics personnel, PCPs, CMAs, and patients through meetings to identify potential influences of implementation of this project. **Pilot Testing:** All CP- CDS algorithms and interfaces will be extensively pilot-tested among stakeholders in Phase 2 to adapt the implementation. Representatives from EH Patient Councils will evaluate the patient interfaces to maximize patient-centeredness. We will then recruit two EH clinics not in the study and pilot test CP-CDS in eligible patients for 4 weeks. We will conduct in-depth interviews with up to 10 PCPs at the two pilot clinics pre- and post-pilot, asking probing questions about shared decision-making and shared decision-making tools. After further modification of the CP-CDS, the project will enter Phase 3. **EH Patient Advisory Councils:** EH has 18 volunteer patient advisory councils that engage patients and families as advisors, mentors, and educators. The main goal of this program is to improve the patient and family experience and quality of healthcare. Research team members will recruit representative members to regularly review and critique project pilot phase activities, CDS interfaces, survey tools, interview objectives and results, and project deliverables. This existing infrastructure is ideal for introducing CDS technology to primary care, gaining the reaction and input of patients and families, and refining adaptation of the intervention.

**Implementation of the Cluster-Randomized Trial (Phase 3):** We will train intervention clinics to use CP-CDS using strategies similar to those EH routinely uses to inform clinic teams of changes to the EHR. They include face-to-face group or individual meetings with all intervention clinic PCPs, CMAs, and clinic staff, plus email reminders with links to a short instructional video demonstrating CMA and PCP roles in CP-CDS use. Training will be completed and CP-CDS fully implemented at the 24 intervention clinics within 30 working days of the project "go-live" date.

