#### 4.9.3 Aim 2 Analytic Approach

**12-Month Utilization (H3):** Incremental medical costs will be estimated using standard health econometric methods. A generalized estimating equation (typically assuming a gamma distribution and log link function) will be used to estimate costs by study arm while allowing clustering by clinic and controlling for demographics and baseline clinical risk factors. The marginal effect of being assigned to an intervention clinic will provide an estimate of the incremental medical cost associated with the CP-CDS intervention. Urban and rural clinic- based eligible subjects receiving care from eligible PCPs will also be

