Coronary Heart Disease Status	Indicator variable for CHD comorbidity based on one or more inpatient or outpatient ICD-9 codes 410.xx-414.xx or 429.4 (To be updated to ICD-10 codes.)	Wizard EHR Diagnosis Codes,	Nominal
Diabetes Status	Indicator variable for diabetes mellitus based on inpatient and outpatient diagnosis codes, filled prescription for a glucose-lowering medication other than metformin or TZD, and/or laboratory tests that indicate diabetes; or a combination of these. Validated in DK06650 and DK068314.	Wizard EHR Diagnosis Codes	Nominal
Hospice Care	In a defined period of time, one or more HPMG special codes for Hospice Care on EHR Problem List. Exclusion criteria for study eligibility.	Wizard EHR	Nominal
Alzheimer's Disease Status	Indicator variable for Alzheimer's disease based on one or more inpatient or outpatient ICD-9 codes	Wizard EHR	Nominal

Number of Office Visits	Outpatient primary care visits, in a defined period of time.	Wizard EHR	Interval
-------------------------	--	------------	----------

CDS Activations	Count of CDS activations within 12 months of the patient index date within the intervention arms	CDS	Interval
Index date for patients age 9-17	First date on which a patient age 9-17 has a primary care visit and is due for HPV vaccination	EHR	Date
BPA fire for patients age 9-17 for HPV vaccination	Indication that the “needs HPV vaccination” Essentia Health BPA fired at the index encounter	Administrative	Binary
Clinic ID	Clinic identification number needed for randomization and for use as a random effect in the analysis.	Wizard EHR and Administrative	Nominal
Dates of HPV vaccination prior to index date	Dates of all HPV vaccination prior to the index date for patients age 9-17	EHR Procedures	Date
Dates of HPV vaccination after index date	Dates of all HPV vaccination in the 12 months following the index date for patients age 9-17	EHR Procedures	Date
Clinic Location: Rural vs. Urban	Based on RUCA2-UR codes	Administrative	Nominal
Provider Type	Primary care physician, CMA, other. Used to determine provider study eligibility.	Administrative	Nominal
Provider Department	FP, IM, Med/Peds, Other	Administrative	Nominal
Provider Age	Years	Administrative	Interval
Provider Gender	Male or female	Administrative	Binary

**Figure A.2 Protocol for Cancer Prevention-Clinical Decision Support Implementation Metrics Using the RE-AIM Framework (Tan Shaded)**

Domain	Measure	Data Source

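### The Aim 1 and Aim 2 models cluster on clinic, but 34 clinic units were randomised from 36 clinics and no analysis level is defined for those units

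*Combined protocol and SAP*

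**What the plan says.** The design separates clinics from randomised units. Specific Aim 1 describes "34 randomized clinic units, with 3 clinics randomized together due to shared providers". Section 1.3 gives the units by arm: "11 intervention clinic units in the PCP-focused group, 11 intervention clinic units in the SDMT-focused group, and 12 usual care control clinic units". Section 3.3 repeats that there are 34 randomised units.

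The analysis text does not carry this distinction over.

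- **H1 and H2 (Section 4.9.1).** The model is justified with "Because clinics are the unit of randomization and the outcome varies at the level of the patient". "Random terms are included for clinic", provider and patient; there is no term for the randomised unit. The provider term is dropped if its ICC is below 0.005.
- **Appendix A, Figure A.1.** Clinic ID is described as "Clinic identification number needed for randomization and for use as a random effect in the analysis".
- **H3 (Section 4.9.3).** A GEE "will be used to estimate costs by study arm while allowing clustering by clinic". The H4 model in the same section also clusters by clinic.

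Two further counts matter. Section 4.6 has "CP-CDS fully implemented at the 24 intervention clinics within 30 working days". Section 3.3 says "The 12-usual care (UC) clinics for the Cardiovascular Wizard studies will continue as control clinics".

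**The concern.** In a cluster-randomised trial the analysis should recognise the unit that was allocated. Here one allocated unit is made up of three clinics, grouped because they share providers, and shared providers are a plausible source of correlated screening and vaccination rates. If each clinic is its own cluster, one randomised unit counts as three independent pieces of evidence. The arm that holds it then appears to carry more information than it does, and tests of that arm against usual care, or against the other CDS arm, lean towards false positives.

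The Aim 1 provider term is not a dependable safeguard. The text indexes it within clinic, and it may be removed. Section 4.9.3 describes no provider term for Aim 2.

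**Working it through.** **1. Where the three clinics sit.** Clinics: 36 in total, 12 usual care (Section 3.3), 24 intervention (Section 4.6); 24 + 12 = 36. Units: 11 + 11 + 12 = 34 (Section 1.3). Usual care has 12 clinics in 12 units. The CDS arms have 24 clinics in 22 units. One group of three accounts for the difference of two, so one CDS arm has 13 clinics in 11 units and the other has 11 in 11.

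**2. The plan's own figures (Section 4.9.2).** Effective n = n / [1 + (n/k − 1) × ICC], with k = 10 clinics per arm.

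- H1: n = 3,133 + 11,088 = 14,221. This gives 483.3 at ICC 0.02 and 1,754.5 at ICC 0.005; the plan states 484 to 1,754.
- H2: n = 7,092. This gives 467.7 and 1,561.8; the plan states 468 to 1,562.

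Both ranges reproduce with 10 clusters per arm, fewer than the 11 or 12 units randomised.

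**3. Cluster counts alone.** Taking equal information per cluster, the SE with 13 v 12 clusters relative to 11 v 12 is √[(1/13 + 1/12) / (1/11 + 1/12)] = 0.959, about 4% smaller.

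**4. Allowing for small clinics.** Assumptions: 14,221 H1 patients per arm; 300 patients in each of the three clinics; the other ten units equal in size; ICC 0.02. A cluster of m patients contributes m / [1 + (m − 1) × ICC].

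- Ten other units of 1,332.1 patients: 10 × 48.23 = 482.3.
- The three clinics as one cluster of 900: 47.4. Arm total 529.7.
- The three clinics as three clusters of 300: 3 × 42.98 = 128.9. Arm total 611.2, which is 15.4% more.
- Usual care, 12 equal units: 576.2.
- SE by site relative to SE by unit: √[(1/611.2 + 1/576.2) / (1/529.7 + 1/576.2)] = 0.965.

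**5. Why the error rate can rise more than a 4% shortfall implies.** Splitting the group also gives it too much weight in the arm mean. If the three clinics share one cluster effect, the true variance of that mean is 1/611.2 + 6 × 42.98² × 0.02 / 611.2² = 0.00164 + 0.00059 = 0.00223. The site-coded model reports 0.00164. Adding usual care (1/576.2 = 0.00174), the reported SE is √(0.00337 / 0.00397) = 0.922 of the true one. A nominal two-sided 0.05 contrast then runs at 2 × P(Z > 1.96 × 0.922) = 0.071.

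The same calculation over a range of assumed sizes, with a fully shared effect:

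| ICC | Patients per grouped clinic | Information overstated | SE by site / SE by unit | Type I error at nominal 0.05 |
|---|---|---|---|---|
| 0.005 | 80 | 3.4% | 0.991 | 0.053 |
| 0.005 | 600 | 14.2% | 0.967 | 0.068 |
| 0.02 | 80 | 9.8% | 0.976 | 0.062 |
| 0.02 | 300 | 15.4% | 0.965 | 0.071 |
| 0.02 | 600 | 17.0% | 0.961 | 0.0735 |

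**6. Simulation under the null.** This used 40,000 runs per setting, a random-effects analysis of cluster means, about 38,000 records, an 11% event rate, ICC 0.005 to 0.02, and each grouped clinic one tenth or one third of a typical cluster. Type I error at nominal 0.05 for that arm against usual care, coded by site:

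- group effects independent: 0.050;
- half shared: 0.050 to 0.063;
- fully shared: 0.054 to 0.072.

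Coded by the 34 units it stayed between 0.047 and 0.053.

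**The case against.** The strongest reply is that the plan never specifies a 36-level model. Figure A.1 ties Clinic ID to randomisation, which can be read as the unit identifier. The rural, micro, small-town and urban counts of clinics in Section 3.3 (10 + 7 + 8 + 9) add to 34, so the documents sometimes use the word clinic for the randomised unit. The 36 clinics in Figure A.3 belong to a lookup of rurality codes, not a model. This stands: the fault is an undefined cluster variable whose literal reading gives 36 levels.

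Several other limits also stand.

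- **Correlation is required.** Joint allocation alone does not bias a model-based standard error. The inflation needs both site-level coding and correlation among the three clinics.
- **The plan's decision rule is stricter than one contrast.** Section 4.9.1 applies P<0.025 to the overall treatment effect and also requires positive, significant terms for both arms. A normal-approximation check, assuming two-sided 0.05 for each term because no level is given, puts the chance of falsely declaring H1 supported at about 0.0026. It rises to at most about 0.0032 over the settings in the table above.
- **No degrees-of-freedom method is stated.** A contrast of 33 (36 − 3) with 31 (34 − 3) matters only if between-cluster degrees of freedom are used.
- **The provider index is printed inconsistently** between the equation and the text. With one ID per provider across the three clinics, the term could absorb part of the shared correlation in Aim 1.
- **The location of the group is inferred** from the counts, which must be read as sites.

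None of this supplies the missing definition. The index file in Figure A.3 carries a visit location, and no randomisation-unit field is listed, so coding by site remains an easy outcome.

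**Conclusion.** The concern holds as a gap in the specification, with a small and conditional effect. The analysis sections name clinic as both the randomised unit and the cluster, while the design randomised 34 units from 36 clinics. If coding is by site, the SE of contrasts involving one CDS arm is up to about 4% smaller than in the analysis by unit. The type I error of such a contrast is about 0.05 to 0.07 at nominal 0.05. These figures rest on H1 counts, the plan's ICC range, and assumed sizes and correlation for the three clinics. No equivalent figure was worked out for H2 or for the Aim 2 cost and coding models, although the definition is missing there too.

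A reader might infer that the plan credits one arm with 13 independent clusters, that its standard errors are certainly too small, or that the trial is underpowered. The documents support none of these. The number of cluster levels is never stated, there is no inflation if the three clinics are uncorrelated, and the sample size uses 10 clusters per arm. Severity is minor; this is a free improvement.

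**What to change.** - Add a randomisation-unit ID with 34 levels to the analysis file, with the three grouped clinics under one value.
- Use it as the top-level random effect for H1 and H2 and as the GEE cluster for H3 and H4.
- Give each provider a single ID across the three clinics.
- Base any between-cluster degrees of freedom on the 34 units.
- Reword Section 4.9.1 and the Clinic ID entry in Figure A.1 to refer to the 34 clinic units, and make the same change to the clustering statements in Section 4.9.3.

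The cost is one variable and a few words; no extra data or patients are needed. If the team already codes it this way, one sentence saying so closes the point.

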**Hypothesis 2:** From the preliminary data pull, we estimate that 21,277 patients (7092 per study arm) aged 11-26 with clinic visits over 18 months have not received all 3 HPV vaccinations and associated with an estimated 75% of providers. The proportion of patients with all 3 HPV vaccinations is currently 19.5% for females and 5.1% for males (12% pooled). Among those without all 3 HPV vaccinations and thus study eligible, the anticipated pattern of effects for receipt of all 3 HPV vaccinations is shown in Table 3 (20% UC, 33% PCP CDA, 40% SDMT CDA). The effective sample size for the analysis is reduced to 468-1562 per arm due to anticipated ICCs of 0.005 to 0.02, reflecting the clustering of patients within clinics. With this range of effective sample sizes and 10 clinics per arm, we will have 80% power ( $\alpha_2=0.05$ , R square of HPV vaccination with other covariates from 0 to 0.1) to detect a minimum detectable difference of completion of all 3 HPV vaccinations at 18 months following patient index visits of 20% (pooled female and male) in patients seen in UC clinics and 26.0%-31.3% for patients seen in clinics assigned to the PCP CDS study arm. Therefore, we anticipate adequately powered minimum detectable effect sizes in the anticipated pattern of effects for a range of ICCs and contributions of other variables such as patient sex to the prediction of the study endpoint.

